4.2.2 Serious adverse events

A serious adverse event is any untoward medical occurrence or effect that at any dose:

- results in death;
- is life threatening (at the time of the event);
- requires hospitalisation or prolongation of existing inpatients' hospitalisation;
- results in persistent or significant disability or incapacity;
- is a congenital anomaly or birth defect.

Any other important medical event that may not result in death, be life threatening, or require hospitalization, may be considered a serious adverse experience when, based upon appropriate medical judgement, the event may jeopardize the subject or may require an intervention to prevent one of the outcomes listed above.

All serious adverse events have to be reported to the sponsor within 24 hours, by fax or email or via a specific designed form.

The sponsor will report the SAEs through the web portal *ToetsingOnline* to the accredited MEC that approved the protocol, to the competent authority, the Medicine Evaluation Board, and the competent authorities in other member states. The expedited reporting will occur within 15 days after the sponsor has first knowledge of the serious adverse reactions.

SAEs that result in death or are life threatening should be reported expedited. The expedited reporting will occur not later than 7 days after the responsible investigator has first knowledge of the adverse reaction. This is for a preliminary report with another 8 days for completion of the report.

4.3 Follow-up of adverse events

All AEs will be followed until they have abated, or until a stable situation has been reached. Depending on the event, follow up may require additional tests or medical procedures as indicated, and/or referral to the general physician or a medical specialist.

4.4 Source data identification

Patient information collected in the eCRF, but not recorded in the patients' file is regarded as source data. Information that should be collected in both the eCRF and the patient files include visit dates, safety data (including AEs and SAEs), withdrawal of consent, and any information on violating the study procedures prior to obtaining informed consent. Patients' files should also include a statement of participation in this trial, along with a copy of the signed informed consent form. Copies of biopsy report from local pathologists will be filed in the eCRF.

5. STATISTICAL ANALYSIS

5.1 Primary study parameters

The primary end point will be analysed by testing the following hypothesis.

The proportions of patients in either Arm A or Arm B who have recurrence of bladder cancer at one year after TURB will be compared. A two-sided test will be used, with the accompanying null-hypothesis being:

H_0 : The proportions of subjects with recurrence of bladder cancer at one year after TURB are equal for Arm A and Arm B, i.e. $H_0: \pi_A = \pi_B$;
with subsequently, $H_1: \pi_A \neq \pi_B$.

An intention-to-treat analysis will be performed, meaning that all subjects who were randomized will be included in the analyses.

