1. INTRODUCTION AND RATIONALE

Urothelial carcinoma (UC) develops in the bladder and the upper urinary tract (UUT). Non-muscle-invasive bladder cancer (NMIBC) includes stages Ta, T1 and carcinoma in situ (CIS) and it accounts for 75% of primary diagnosed bladder tumors. Recurrence rates of UC are exceptionally high, which calls for extensive diagnostics and surveillance strategies.

Percentages on recurrence from EORTC studies have been estimated to range from 15% to 61% at one year after surgery. Risk for recurrence is associated with stage, grade and number of tumors, while progression is associated with grade and the presence of CIS (Sylvester et al., 2006).

Diagnostics of UC of the bladder is usually performed by the visual approach including the need for biopsies or transurethral resection of the bladder (TURB). Most tumors can be identified by White Light (WL) cystoscopy. However, especially CIS is difficult to identify using this procedure. Non-identified tumors can later appear as recurrence, some of which becoming invasive. This demonstrates the need for a procedure that more accurately detects bladder tumors. Since a more accurate detection of tumors leads to more targeted treatment and better complete resection, the rate of recurrence may decrease with such procedures.

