2.5 Justification of sample size

Sample size is based on the subgroup analysis of patients with primary tumors. The normal approximation to the binomial distribution was used, using continuity corrected Chi square test for proportions, and the following specifications were set:

- a. Randomization rate between the two arms= 1:1

- b. Clinically relevant difference in recurrence detection rates $\geq 10\%$
- c. Significance level (α - two sided) = 5%
- d. Power ($1-\beta$) = 80%
- e. Expected recurrence rate at 1 year in the control arm (Arm B) = 35% (Babjuk et al., 2013).

The required sample size per arm is calculated to be 349 patients, which leads to a total of at least 698 patients needed to detect the difference in proportions stated above for the subgroup analysis of only patients with primary tumors. Since we expect approximately 15% of the patients to be misdiagnosed, and thus not suitable to our research question, the number of patients is inflated with that percentage, leading to 401 patients per arm. Additionally, to allow for a non-compliance rate of 20%, assuming no cross-over and no differential loss to follow up between the arms, the calculated sample size is inflated by 20%, yielding 482 patients per arm. Since approximately $\frac{1}{2}$ of all patients will be patients with primary tumors, this sample size is multiplied by two, leading to a total sample size of 1,928. Sample size calculation was performed using nQuery Advisor 7.0.

TREATMENT OF SUBJECTS

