3.4.8 Study duration (patient)

Patients participating in this study will undergo a screening visit, followed by SPIES or WLI assisted TURB. During TURB, cystoscopy will be performed and biopsies and resections will be taken for analysis. Several follow up visits will be planned (at three, six, nine and twelve months and 18, 24, 30 and 36 months after TURB) to check for possible recurrence of the tumors. Depending on the grade and stage of the (initial or recurrent) tumors, these visits could be scheduled more often if the treating physician deems necessary.

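### The one-year comparison of crude proportions has no sound place for patients lost before month 12; a Kaplan-Meier 12-month difference would use their clear cystoscopies without changing the hypothesis

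*Protocol*

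**What the plan says.** Protocol section 5.1 sets the primary analysis as a two-sided comparison. The proportions of patients in either arm "who have recurrence of bladder cancer at one year after TURB will be compared", with the null hypothesis that "The proportions of subjects with recurrence of bladder cancer at one year after TURB are equal for Arm A and Arm B". The section calls this an intention-to-treat analysis, "meaning that all subjects who were randomized will be included in the analyses". It names no test. The only test named is in section 2.5, where the sample size is derived "using continuity corrected Chi square test for proportions", and "Sample size is based on the subgroup analysis of patients with primary tumors".

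Section 3.4.8 gives the schedule: "Several follow up visits will be planned (at three, six, nine and twelve months and 18, 24, 30 and 36 months after TURB". Sections 3.4.3 to 3.4.5 require visible lesions at these visits to be confirmed histologically, and section 4.4 has visit dates recorded in the eCRF. The time of first recurrence, to the nearest visit, is therefore already collected.

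For a missing primary outcome, section 5.4 gives a sensitivity analysis only. A missing month-12 result is set to recurrence unless a later visit shows none. Section 2.5 enlarges the sample "to allow for a non-compliance rate of 20%, assuming no cross-over and no differential loss to follow up between the arms". The protocol states no rate or timing of loss to follow-up.

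**The concern.** A crude proportion at one year needs a one-year status for everyone in its denominator. A patient with clear cystoscopies at months 3, 6 and 9 who is then lost has none, yet section 5.1 promises to include all randomised subjects. There are three ways to proceed:

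- drop the patient, which breaks that promise and wastes three clear visits;
- keep recurrences seen before loss and choose a denominator, which biases the 12-month proportion up or down;
- score the patient as a recurrence, as the sensitivity analysis does when no later clear visit exists.

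At stake are the reported 12-month recurrence in each arm, its difference, and a few points of power in the primary-tumour subgroup on which the trial is sized.

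**Working it through.** **Inputs from section 2.5.** Control recurrence 35%, difference 10 points (so 25% under SPIES), two-sided alpha 5%, power 80%, allocation 1:1, inflation for 15% misdiagnosed and then for 20% non-compliance.

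**Assumptions not in the protocol.** The 20% is loss to follow-up, spread evenly over the year: a quarter of lost patients attend none of the four visits, a quarter one, a quarter two and a quarter three. Loss is unrelated to recurrence. The hazard is constant in each arm. Recurrence at one year means a first confirmed recurrence at any visit up to month 12.

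**1. The plan's own figure.** Without continuity correction, n = [1.960√(2 × 0.30 × 0.70) + 0.842√(0.35 × 0.65 + 0.25 × 0.75)]² / 0.10² = 328.5, so 329. With correction, n′ = (328.5/4)[1 + √(1 + 4/(328.5 × 0.10))]² = 348.2, so 349, as stated. Then 349 × 1.15 = 401, 401.35 × 1.20 = 482, and 482 × 4 = 1,928. The sizing reproduces.

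**2. Bias from counting lost patients in a crude proportion.** Cumulative recurrence at month t is 1 − 0.65^(t/12) for WLI and 1 − 0.75^(t/12) for SPIES.

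| | 3 mo | 6 mo | 9 mo | 12 mo | Seen before loss, lost patients |
|---|---|---|---|---|---|
| WLI | 0.102 | 0.194 | 0.276 | 0.350 | (0 + 0.102 + 0.194 + 0.276)/4 = 0.143 |
| SPIES | 0.069 | 0.134 | 0.194 | 0.250 | (0 + 0.069 + 0.134 + 0.194)/4 = 0.099 |

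Events observed per patient randomised:
- WLI: 0.8 × 0.35 + 0.2 × 0.143 = 0.309
- SPIES: 0.8 × 0.25 + 0.2 × 0.099 = 0.220

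The result then depends on the rule for patients lost without an event:

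| Rule | SPIES | WLI | Difference |
|---|---|---|---|
| Truth | 25% | 35% | 10.0 |
| Excluded: 0.220/(0.8 + 0.020); 0.309/(0.8 + 0.029) | 26.8% | 37.2% | 10.4 |
| Counted as recurrence-free | 22.0% | 30.9% | 8.9 |
| All lost set to recurrence: 0.8 × 0.25 + 0.2; 0.8 × 0.35 + 0.2 | 40% | 48% | 8.0 |

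The last row is the section 5.4 rule when lost patients have no later visit. Kaplan-Meier estimates the recurrence probability at each visit among those still under observation, and so returns 25% and 35% under these assumptions.

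**3. Power in the primary-tumour subgroup.** 482 × 0.85 = 410 per arm; with 20% lost, 328 reach month 12.

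- Lost patients dropped: SE = √(0.415/328) = 0.0356, where 0.415 = 0.35 × 0.65 + 0.25 × 0.75. The null SE is √(0.42/328) = 0.0358. Uncorrected power = Φ[(0.10 − 1.96 × 0.0358)/0.0356] = 0.80. Subtracting the correction 1/328 from 0.10 gives 0.77; simulation gave 0.77 to 0.78.
- Kaplan-Meier difference, Greenwood variance S²Σ q/[(1 − q)n_k]. The fractions still attending at the four visits are 0.95, 0.90, 0.85 and 0.80. The variance terms are 0.263 (WLI) and 0.216 (SPIES), each divided by 410. SE = √(0.479/410) = 0.0342 and power = Φ(0.10/0.0342 − 1.96) = 0.83. Simulation gave SE 0.0341 and power of about 0.83.

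The gain is about 3 points over the uncorrected test and about 5 over the corrected one.

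**4. Where the gain is small or absent.**
- With no loss, Kaplan-Meier at month 12 equals the crude proportion, and the gain over the uncorrected test is 0 to 1 point.
- If events seen before loss are kept and patients lost without an event excluded, the crude test simulates at 0.829 under proportional hazards. That leaves little power to gain, but the bias in step 2 remains.
- In all randomised patients (820 per arm, 656 reaching month 12, same rates assumed), power is Φ[(0.10 − 1.96 × √(0.42/656))/√(0.415/656)] = 0.98 for the crude test. For Kaplan-Meier it is Φ(0.10/√(0.479/820) − 1.96) = 0.985.

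**5. Log-rank to month 12, same setting (410 per arm, 20% lost).** Simulated power against the uncorrected proportion in month-12 completers:
- proportional hazards: 0.84 v 0.80;
- early effect: 0.94 v 0.80;
- late effect: 0.70 v 0.80.

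The Kaplan-Meier difference held 0.82 to 0.84 in every timing pattern that was feasible under a constant control hazard.

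**The case against.** The strongest reply is that nothing here is an error. The objective, sizing and hypothesis all concern the proportion recurring by 12 months, and 349 per arm reproduces exactly. Section 5.1 names no test, a Kaplan-Meier difference tests the same hypothesis, and the statistical analysis plan foreseen in section 7.2 may settle the estimator. The 20% is called non-compliance, not loss. Inflation keeps even the completers' test near its planned 80%. All of this stands, and it limits the point to an inefficiency and a gap in handling.

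It does not remove the gap. Read with the test in section 2.5, section 5.1 describes a crude two-proportion comparison. The only stated rule for a missing month-12 result is a sensitivity analysis, and a crude proportion cannot include every randomised patient without one of the choices shown above.

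A reader might infer something stronger. The introduction says "Non-identified tumors can later appear as recurrence, some of which becoming invasive", which suggests an early effect, and it is tempting to conclude that the fixed-time test forfeits well over ten points of power and that log-rank should be primary. The protocol does not support this. It states no timing of the effect and no loss rate. The log-rank figures run from about +14 points (early effect) to −10 (late effect), so they are not a cost of the plan. Nor is the proportion test weaker when the effect is early: its power stays at about 0.80, because early recurrences still count by month 12.

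**Conclusion.** The point holds as a matter of estimation and handling of partial follow-up. Serial, dated cystoscopies are collected, but the stated primary comparison makes no use of them for patients lost before month 12. With 20% lost evenly over the year, a crude proportion that keeps early events misstates 12-month recurrence by about 2 points upwards in each arm, or by 3 (SPIES) to 4 (WLI) points downwards. Dropping lost patients instead costs about 3 points of power in the primary-tumour subgroup against the Kaplan-Meier difference, or about 5 if the continuity correction is used.

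These sizes rest on reading the 20% as loss spread over the year and unrelated to recurrence. They shrink towards nothing as loss falls, and for all randomised patients the power gain is negligible. The change is worth making because it costs almost nothing, not because the trial is underpowered.

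**What to change.** In section 5.1 keep the 12-month hypothesis and horizon, and change the estimator:

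- Define the event as the first histologically confirmed recurrence at any visit up to and including month 12, with its four-week window.
- Estimate 12-month recurrence in each arm by Kaplan-Meier on scheduled visit time, censoring patients without recurrence at their last clear cystoscopy. A patient who misses month 12 but is clear at a later visit then counts as recurrence-free at month 12, in line with section 5.4.
- Test the difference in 12-month recurrence and report it with a 95% confidence interval.
- Keep the crude proportion and the section 5.4 sensitivity analysis as supportive.
- A log-rank test truncated at 12 months may be added as supportive, not as the primary test, because its gain or loss depends on when the effect appears.

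The cost is wording in the protocol or the statistical analysis plan, with no new data, visits, patients or delay. The small downside is the assumption that censoring is unrelated to recurrence given follow-up so far, which is why the sensitivity analysis stays.

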Rationale: Urothelial carcinoma of the bladder has a high recurrence rate, partly due to missed lesions at diagnostics with White Light Imaging (WLI) cystoscopy. Storz Professional Image Enhancement System (SPIES) is a new technique that visually enhances the images in order to improve diagnostic accuracy. SPIES assisted TURBs are expected to result in lower recurrence rates of bladder tumor compared with White Light TURBs.

Objective: To compare the recurrence rate of tumor at 12 months following SPIES assisted TURB with WLI assisted TURB in patients with non-muscle invasive bladder cancer (NMIBC Ta/T1/CIS).

Study design: This study is a multicenter randomized controlled trial in which the efficacy between SPIES assisted and WLI assisted TURB are compared. Subjects in the experimental arm (Arm A) will undergo SPIES assisted TURB, whereas subjects in the control arm (Arm B) will receive treatment with WLI assisted TURB only. Baseline characteristics will be recorded, as well as short and long-term follow up.

Study population: The study population comprises those patients who are presenting with primary or recurrent urothelial bladder cancer (NMIBC stage Ta, T1 or CIS) in the participating centers.

Intervention: All patients will undergo TURB. Patients in Arm A will undergo SPIES and WLI assisted TURB, and patients in Arm B will undergo WLI only assisted TURB.

Main study parameters/endpoints: Primary end point of the study is recurrence rate of tumor at 12 months after TURB in the two arms. Secondary end points include recurrence rates at 3 months and 3 years.

Nature and extent of the burden and risks associated with participation, benefit and group relatedness: The burden and risk associated with participating in this trial does not differ for patients in the experimental or the control arm. In both groups patients will undergo TURB, and will be followed for a maximum of three years at several site visits, in accordance with existing guidelines for follow up.

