3. METHODS

3.1 Study parameters/endpoints

3.1.1 Main study parameter/endpoint

- Comparison of the proportions of Arm A and Arm B subjects who undergo TURB for a Ta, T1 or CIS bladder tumor that have a histologically confirmed recurrence found at either three months, one year and three years after TURB.

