At three months after surgery, all patients will undergo a routine follow up using WLI cystoscopy. A two-week window will be allowed for the timing of this examination. All visible lesions should be confirmed histologically. Adjuvant treatment will be offered according to the local protocols. When appropriate, information on re-TUR and/or adjuvant treatment will be recorded, as well as adverse events. Information on re-TUR includes reasons for performing this procedure to determine if it was an incomplete resection or a true recurrence found at follow up. Information on adjuvant treatment includes type, timings, time limits and dose.

3.4.4 Intermediate follow up – 6, 9, 12, 18, 24 and 30 months after surgery – Visit 4 to 9

At the time points specified above, all patients will undergo a follow up using WLI cystoscopy. A four-week window will be allowed for the timing of this examination. All visible lesions should be confirmed histologically.

3.4.5 Last study follow up – three years after surgery – Visit 10

At three years after surgery, all patients will undergo a follow up using WLI cystoscopy. A four-week window will be allowed for the timing of this examination. All visible lesions should be confirmed histologically.

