5.4 Handling missing and spurious data

When missing data occurs in the primary outcome variable, a sensitivity analysis will be performed. In the sensitivity analysis, the missing data at three months will be substituted by the value "recurrence", unless the result at later follow up is "no recurrence". Missing data at twelve months will be substituted by the value "recurrence", unless the result at later follow up is "no recurrence". Missing data at three years will be substituted by the value "recurrence". In the analyses of secondary objectives, analyses will be carried out on available data, with reporting of proportions of missing data.

All analyses will be performed using software SPSS 20, Stata 13 and R 3.0 or higher. Analysis will be based on the principle of intention-to-treat. All patients who signed the

informed consent form, met the study entry criteria and underwent randomization will be included in the analysis.

Results will be presented in tables reporting at least the number of subjects, mean, standard deviation, minimum and maximum for continuous data; and number of subjects and percentages for categorical data.

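### The primary endpoint is worded inconsistently and never made cumulative, so the protocol does not say whether a recurrence confirmed before month 12 counts

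*Protocol*

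**What the plan says.** - **Summary:** "Primary end point of the study is recurrence rate of tumor at 12 months after TURB in the two arms". Section 2 (Objectives) likewise compares recurrence at 12 months, and makes 3 months and 3 years secondary.
- **Section 5.1:** the null hypothesis concerns the proportions of patients "who have recurrence of bladder cancer at one year after TURB will be compared".
- **Section 3.1.1**, the only operational definition, compares the proportions with a "histologically confirmed recurrence found at either three months, one year and three years after TURB".
- **Section 3.4.4** is headed "Intermediate follow up – 6, 9, 12, 18, 24 and 30 months after surgery – Visit 4 to 9". It requires that "At the time points specified above, all patients will undergo a follow up using WLI cystoscopy" and that "All visible lesions should be confirmed histologically".
- **Section 3.4.8** lists visits at 3, 6, 9 and 12 months and beyond, and adds that "these visits could be scheduled more often if the treating physician deems necessary".
- **Section 5.4**, for a sensitivity analysis: "Missing data at twelve months will be substituted by the value" recurrence, unless the result at a later follow-up is no recurrence. Earlier findings are not mentioned.

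**The concern.** Between TURB and month 12 the schedule has cystoscopies at 3, 6, 9 and 12 months, with more allowed. A recurrence seen at one of the earlier visits will normally be resected; section 3.1.2 itself foresees a repeat resection for a recurrent tumour confirmed at three months. Such a patient can be clear at 12 months. If the endpoint is status at the one-year visit, that patient has no event. If section 3.1.1 is read as a list of countable visits, a recurrence first found at 6 or 9 months, or at an unscheduled examination, also drops out.

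This matters because section 1 gives missed lesions and incomplete resection as the reason to expect a benefit. Recurrences before month 12 are among the events that SPIES is meant to prevent. Two analysts following sections 3.1.1 and 5.1 could score the same patient differently, in a trial whose surgeons are not blinded (section 3.3).

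**Working it through.** **1. What the wording gives for particular patients.**

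| Patient | Status at the one-year visit | 3- and 12-month visits only | Cumulative to month 12 |
|---|---|---|---|
| Confirmed and resected at 3 months, clear at 12 | no event | event | event |
| Confirmed and resected at 6 or 9 months, clear at 12 | no event | no event | event |
| Confirmed at 12 months | event | event | event |

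No section says which column applies. Under section 5.4, take a patient with a confirmed recurrence at 6 months, a missed 12-month visit and a clear 18-month visit. The exception applies, so recurrence is not substituted and the patient is in effect scored as no recurrence, despite the confirmed event.

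**2. The plan's own sample size.** Inputs from section 2.5: control rate 35%, difference 10 points, two-sided α 5%, power 80%, 1:1 allocation, continuity-corrected test. The 25% for Arm A is not printed. It is implied by the difference and confirmed by the result: 35% vs 25% gives 349, whereas 35% vs 45% would give 396.

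Uncorrected: n₀ = [1.960·√(2·0.30·0.70) + 0.842·√(0.35·0.65 + 0.25·0.75)]² / 0.10² = 328.5.

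Corrected: n = (n₀/4)·[1 + √(1 + 4/(n₀·0.10))]² = 348.2, rounded up to **349**, as stated. The chain follows: 349 × 1.15 ≈ 401; 401 × 1.2 = 481.2, rounded up to 482; 482 × 2 arms × 2 = 1,928.

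**3. Power if only part of the recurrences is captured.** Let f be the share of one-year recurrences that the definition captures, assumed equal in both arms. The protocol gives no timing, so f is an assumption. Then p₁ = 0.35f, p₂ = 0.25f, p̄ is their mean, and

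power = Φ{[(p₁ − p₂ − 1/n) − 1.960·√(2p̄(1−p̄)/n)] / √([p₁(1−p₁) + p₂(1−p₂)]/n)}.

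For f = 1 and n = 349: (0.0971 − 1.960 × 0.0347)/0.0345 = 0.845, power 80.1%. For f = 0.5: (0.0471 − 1.960 × 0.0270)/0.0270 = −0.217, power 41%.

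The primary objective covers all patients, so a second column uses 655 per arm. This figure is not in the protocol. It is 1,928/2 = 964, times 0.85 for misdiagnosis and 0.80 for non-compliance, = 655.5.

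| f | Arm B vs Arm A | Power, 349 per arm | Power, 655 per arm |
|---|---|---|---|
| 1 (cumulative) | 35% vs 25% | 80% | 97% |
| 0.9 | 31.5% vs 22.5% | 74% | 95% |
| 0.75 | 26.3% vs 18.8% | 63% | 89% |
| 0.5 | 17.5% vs 12.5% | 41% | 69% |
| 0.25 | 8.8% vs 6.3% | 20% | 36% |

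If recurrences were first detected evenly over the four visits and all cleared by resection, f = 0.5 would correspond to counting the 3- and 12-month visits, and f = 0.25 to the 12-month visit alone.

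**4. A case with no loss.** Suppose the whole 10-point effect appears at 3 months and recurrences at 6 and 9 months are equal in the arms, for example 21% vs 11% over the 3- and 12-month visits. Counting those two visits then keeps the full difference, and power at 349 per arm is 94%.

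**The case against.** A reader might infer that recurrences at 6 and 9 months are excluded and that the planned 35% vs 25% contrast is therefore lost. The protocol does not support that.

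- No section states an exclusion. Recurrence at one year is common shorthand for a cumulative rate, and sections 1 and 2.5 use the same wording for the background and planning rates. If the endpoint is read as the 35% is read, the two match. **This stands:** the text is ambiguous, not settled.
- Section 3.1.1 can be read as a list of horizons for the primary and secondary objectives, since a three-year finding cannot feed a one-year endpoint. **This is reasonable**, but the list then sits wrongly under the main endpoint and still does not say what counts up to each horizon.
- Section 5.4 overrides no observed result. It replaces missing values only, in a sensitivity analysis, and letting a later clear result resolve an earlier gap makes better sense if that result means recurrence-free until then. **This stands**, so 5.4 is not proof of a visit-status endpoint. It still ignores an earlier confirmed recurrence.
- The power losses rest on assumed timing and clearance, and the subgroup size of 349 is not the size of the full population. **This stands.**
- Counting rules are often left to a SAP, which is not shown. The protocol, however, does define its primary endpoint and does so inconsistently; that belongs in the protocol.

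**Conclusion.** The defect is real and lies in the definition. The Summary and sections 2 and 5.1 give a time point without a cumulative rule. Section 3.1.1 gives three time points for a one-year endpoint and does not name examinations at which recurrences will be found. Followed literally, the text can score a patient with a confirmed recurrence as recurrence-free, both in the main analysis and in the 5.4 sensitivity analysis.

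The cost cannot be fixed from the protocol. It ranges from none, if the text is applied cumulatively or the effect falls at visits that are counted, to severe if only the 12-month visit counts. The 41% and 69% figures hold only if half of the one-year recurrences are captured, equally in both arms; 69% also assumes 655 evaluable patients per arm. They show why the point should be settled before outcomes are compared, and do not predict this trial's power.

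**What to change.** 1. In sections 3.1.1 and 5.1, define the primary endpoint as any histologically confirmed recurrence at any scheduled or unscheduled examination after TURB, up to and including the 12-month visit window. Once confirmed, it counts permanently. Use the same wording in the Summary and section 2.
2. Define the 3-month and 3-year endpoints in the same cumulative way and move them to the secondary endpoints in section 3.1.2.
3. In section 5.4, state that a confirmed recurrence at any earlier examination makes the patient an event at every later horizon, and that a later clear visit cannot override it.

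A time-to-first-recurrence analysis could be added as support, but it is optional and its absence is not an error.

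The cost is wording only. The scheduled cystoscopies and histology are already required; the case report form need only record the date and histology of recurrences found at unscheduled examinations. The 35% vs 25% inputs, 349 per arm and the total of 1,928 stand.

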3.3 Randomisation and treatment allocation

Patients presenting with a bladder cancer and who are scheduled for TURB or patients who are scheduled for random biopsies and/or TURB because of a bladder wash out or voided urine with malignant (G3) cells will be included in the study. Eligible patients who are willing to participate will be randomized in a ratio of 1:1 to either Arm A (SPIES+WLI assisted TURB) or Arm B (WLI assisted TURB). The CROES will utilize the randomization to minimize systematic error and potential selection bias by the investigators. The randomization will be performed by using randomly permuted blocks (computer generated), with block size of 6. To assure balanced characteristics and comparable prognosis between the two arms, the

randomization will be stratified on tumor multiplicity (single or multiple), tumor status (primary or recurrence) and macroscopic findings at time of baseline visit (papillary or solid/flat tumor [including CIS]), leading to 8 stratification groups.

Concealment of treatment allocation is achieved by: 1) reducing the time between randomization and intervention, 2) first deciding whether the patient meets all study entry criteria, and 3) if so, randomize the patient in the DMS. The randomization will take place just before the intervention starts; ideally both occur on the same day. The DMS performs the randomization then reveals treatment allocation. The patients will be blinded to their allocation. Due to the nature of the procedure, the surgeon will not be blinded.

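### The primary analysis set is worded inconsistently (5.1, 5.4, 3.1.1), and the sample size in 2.5 is coherent only if patients whom 5.1 keeps leave the analysis

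*Protocol*

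**What the plan says.** - **Protocol 5.1:** "An intention-to-treat analysis will be performed, meaning that all subjects who were randomized will be included in the analyses".
- **Protocol 5.4** repeats the intention-to-treat principle, but the patients counted are those who signed the "informed consent form, met the study entry criteria and underwent randomization will be included in the analysis".
- **Protocol 3.1.1** defines the main endpoint as a proportion among "subjects who undergo TURB for a Ta, T1 or CIS bladder tumor".
- **Protocol 2.5:** "Sample size is based on the subgroup analysis of patients with primary tumors", "using continuity corrected Chi square test for proportions". The inputs are 35% vs 25% recurrence at one year, two-sided 5%, 80% power and 1:1 allocation, giving 349 per arm. The text continues: "Since we expect approximately 15% of the patients to be misdiagnosed, and thus not suitable to our research question". This takes 349 to 401. A further 20% for non-compliance, assuming no cross-over and no differential loss to follow-up, gives 482. Doubling for the share of primary tumours gives 1,928 in total.
- **Protocol 2.3 and 3.3:** the disease criterion is being scheduled for treatment of NMIBC, and eligibility is decided before randomisation.
- **Protocol 3.4.6, 2.8 and 3.3:** tissue for staging is taken at the TURB. CIS is expected to be easier to detect with SPIES. The surgeon is not blinded.

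**The concern.** Two analysts citing different sections could form different primary data sets. One keeps every randomised patient, following 5.1. The other treats patients without a confirmed Ta, T1 or CIS tumour as outside the set, citing the entry-criteria condition in 5.4, the denominator in 3.1.1, or the remark in 2.5 that misdiagnosed patients do not suit the research question. By the protocol's own estimate this choice concerns about 15% of patients.

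Two things are at stake. First, confirmed stage comes from tissue obtained after allocation, with a technique that differs by arm and is expected to find more CIS in one of them. Selecting on it could remove different kinds of patients from each arm. Second, 2.5 raises the head count but leaves the 10-point difference undiluted. That arithmetic describes an analysis without the misdiagnosed and non-compliant patients, not the analysis defined in 5.1.

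**Working it through.** **Inputs from 2.5:** p_B = 0.35, p_A = 0.25, two-sided alpha 0.05, power 0.80, 1:1 allocation, continuity correction, 15% misdiagnosed, 20% non-compliant, 482 per arm in the primary-tumour subgroup.

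**Not given (assumption):** the recurrence rate r in misdiagnosed patients. It is taken as equal in both arms and varied from 0% to 61%, the upper end of the one-year range cited in section 1.

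**Step 1: reproduce the stated figures.**
- Uncorrected n = [1.96 x sqrt(2 x 0.30 x 0.70) + 0.84 x sqrt(0.35 x 0.65 + 0.25 x 0.75)]^2 / 0.10^2, which rounds up to 329. With the continuity correction, n = 349, as stated.
- 349 x 1.15 = 401.35 (stated 401). 401 x 1.20 = 481.2, rounded up to 482. 482 x 2 arms x 2 = 1,928. All agree.

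**Step 2: remove both groups, as 2.5 implies.**
- 482 x 0.85 x 0.80 = 328 per arm, below 349. Power at 35% vs 25% is about 77%.
- The shortfall arises because n was multiplied by (1 + d) rather than divided by (1 - d). 349 / (0.85 x 0.80) = 513.2, so 514 per arm would be needed.

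**Step 3: keep the misdiagnosed, as 5.1 requires.**
- p_B = 0.85 x 0.35 + 0.15 r. The difference is d = 0.85 x 0.10 = 0.085, or 0.85 x 0.08 = 0.068 if 20% of Arm A carry the control rate.
- Continuity-corrected power = Phi[(d - 1.96 SE0) / SE1], with pooled SE0 and unpooled SE1 evaluated at n0 = n - 2/d + 1/(n d^2). At n = 349 and d = 0.10 this returns 80.1%, matching 2.5.
- Example with n = 482 and r = 0.35: p_B = 0.350, p_A = 0.265, n0 = 458.8, SE0 = 0.0305, SE1 = 0.0303, power = 79.8%.

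Power in the primary-tumour subgroup:

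| Reading of the 20% | n per arm | r = 0% | r = 35% | r = 61% |
|---|---|---|---|---|
| All analysed, no dilution from non-compliance | 482 | 84.1% | 79.8% | 77.3% |
| 20% without outcome (482 x 0.80) | 386 | 74.8% | 69.9% | 67.2% |
| All analysed, 20% of Arm A at the control rate | 482 | 64.2% | 59.6% | 57.1% |

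No row is fixed by the protocol. The second is not strictly an analysis of all randomised subjects, and the third sits awkwardly with the no-cross-over assumption in 2.5.

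**Step 4: the full-trial comparison in 5.1.** With 964 per arm and the same rates assumed for recurrent tumours, the three rows become 97-99%, 93-97% (n = 771) and 87-92%.

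**Step 5: selection on index histology (illustration).** Suppose SPIES confirms tumour in an extra 2-4% of patients whose recurrence is 50-60%; both figures are assumptions. The Arm A rate in the confirmed set moves from 25% to (0.85 x 0.25 + 0.02 x 0.50) / 0.87 = 25.6%, or to (0.85 x 0.25 + 0.04 x 0.60) / 0.89 = 26.6%. That is a shift of 0.6 to 1.6 points against SPIES with no change in care.

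**The case against.** The strongest defence is that the sections hardly conflict. Eligibility is settled before randomisation on a pre-operative criterion, so a patient with benign histology was still scheduled for NMIBC treatment and satisfies 2.3. On that reading 5.4 differs from 5.1 only for patients randomised in error. Section 3.1.1 defines an endpoint, and its wording may give the indication for TURB rather than a filter on histology. No analysis section orders exclusion on index findings. Section 7.2 foresees a statistical analysis plan, where analysis sets are usually detailed.

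Much of this stands. A reader might infer three incompatible populations, or a rule that excludes patients by arm-dependent histology. The text supports neither; it only permits such an exclusion. What remains is that 5.1 and 5.4 give different conditions under one label, and that 2.5 treats as lost the patients whom 5.1 keeps. A later plan could cite the protocol for either course.

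On power, a reader might take a single band such as 64-75% as the true figure. Its ends come from different meanings of non-compliance, and both ends need misdiagnosed patients never to recur, which the protocol does not say. If all 482 are kept and non-compliance does not dilute, power is 77-84%, close to plan.

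**Conclusion.** The point holds as an inconsistency in the analysis set and a mismatch between that set and the sample size. In the primary-tumour subgroup, on which the whole sample size rests, power with the misdiagnosed kept lies between about 57% and 84%, depending on two quantities the protocol leaves open: recurrence among the misdiagnosed and what non-compliance means. If both groups are removed, it is about 77%. So 80% is reached only if non-compliance neither dilutes the effect nor costs outcomes, and the misdiagnosed recur at less than about 35%.

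A reader might conclude that the primary comparison itself is underpowered. The figures do not support that. At 964 per arm it keeps about 87-99% in the scenarios of step 3, provided recurrent tumours follow the same rates, which 2.5 does not state. Bias from selecting on index histology is a risk opened by the wording; its size rests wholly on assumed inputs.

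**What to change.** 1. Make all randomised subjects, analysed as allocated, the single primary set, as 5.1 already says.
2. In 5.4, delete the entry-criteria condition, or limit it to ineligibility documented from data dated before randomisation.
3. Reword the denominator in 3.1.1 to match.
4. Report the set with histologically confirmed Ta, T1 or CIS as supportive, with the number excluded in each arm.
5. In 2.5, say how misdiagnosed and non-compliant patients are counted, and restate subgroup power as a range with its assumptions.

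As a separate point, 3.3 admits patients "scheduled for random biopsies and/or TURB because of a bladder wash out or voided urine with malignant (G3) cells will be included", while 2.2 expects NMIBC to have been diagnosed after white-light exploration. These two sections must be reconciled.

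The cost is wording in 2.5, 3.1.1 and 5.4 plus one supportive table, with the reconciliation of 3.3 and 2.2 as separate wording. The stated subgroup power will look less favourable under most assumptions. The change should be made before anyone sees outcome data by arm.
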